Stratification: Randomization will be stratified on the presence of major or minor depression (defined by PHQ-9 total score ≥ 5) to ensure equal distribution of depression in the BUSP and placebo groups. This is important since depression is common after TBI, irritability is a primary symptom of depression, and BUSP has potential effect on depression. The study is not designed or powered to examine the effect of BUSP on depression. Participants will

have a 1:1 chance of receiving placebo or active treatment regardless of depression status. Our statistician will create a guide that assists the study pharmacist in the process of carrying out the stratified randomization.

Randomization: After successful screening, enrollment, and stratification, each participant will be assigned a study identification number that determines the double-blind treatment group according to the chronological order of entry into the study. Random assignment to either BUSP or placebo will be based on a computer-generated, block, randomization schedule produced by the statistician and maintained by the study pharmacist. Randomization will be blocked to force balance between the 2 groups (important if the study were stopped). The investigators and study staff will be blinded to the size of the blocks. Upon meeting all eligibility criteria, the RA will fax a completed randomization sheet to the study pharmacist that indicates the information needed for dispensing and stratification (study number, and total PHQ-9 score). The study pharmacist then looks at the randomization schedule and prepares the study medication to be dispensed. The study pharmacist will record the group assignment in the dispensing log.

Compensation: To help offset time and travel costs, participants and their observer will both receive \$50 for the initial formal screening and \$50 for the subsequent visits. Compensation will be provided in the form of check or gas gift card.

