NPI Irritability domain rated by observer. NOTE: The primary analysis looks at the proportion that decrease ≥ 3 points to assess clinical significance in addition to statistical significance. This cut point of clinically meaningful change is based on clinical experience and

consumer input, and was utilized in our previous studies. A secondary analysis compares changes in NPI-Irritability using an ordinal scale.
Secondary Efficacy Measures
NPI- Irritability domain rated by observer and participant
NPI-Distress Irritability domain rated by observer and participant
NPI & NPI-Distress Agitation/Aggression Domain rated by observer and participant
TBI-QOL Anger item bank rated by participant
SASNOS rated by observer
Global Impression of Change rated by observer and participant
Clinical Global Impressions rated by clinician
Working Alliance Inventory – Short Revised rated by participant and Co-Investigator.

Demographic and Pre-treatment Characteristics: Age, gender, marital status, ethnicity, educational level, time since injury, history of psychiatric disorder, previous TBI, cause of injury, CT scan findings, initial Glasgow Coma Scale score in ED, duration of post-traumatic amnesia (PTA), duration of loss of consciousness, socioeconomic status, employment status, substance use during the month prior to enrollment, relationship of observer to subject, medical history, overall function, severity of irritability, and presence of depression, anxiety or post-traumatic stress disorder (PTSD).

Efficacy Measures:

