- **Neuropsychiatric Inventory (NPI & NPI-Distress):** The NPI¹⁰⁴ is a 40-item tool developed to assess behavioral abnormalities in individuals with dementia. Since its development, the NPI has been used in TBI populations to assess neurobehavioral dysfunction.^{23,43,50} It is a fully structured observer interview that specifies verbatim the questions to be asked. The observer indicates if a specific behavior has been present during the past month or specified time period and if this represents a change from premorbid functioning. The most problematic behavior detected by the sub-questions is then used to grade the frequency and severity: behavior severity (1 = mild, 2 = moderate, 3 = severe) and frequency (1 = occasionally, less than once per week; 2 = often, about once per week; 3 = frequently, several times per week, but less than every day; 4 = very frequently, once or more per day or continuously) and the product (severity x frequency) is calculated (range 0-12). The NPI also assesses the caregiver’s distress over the behaviors on a 6-point scale: 0 (no distress), 1 (minimal), 2 (mild), 3 (moderate), 4 (moderately severe), and 5 (very severe or extreme).

For the present study, we will use the NPI Irritability and Aggression domains as outcome measures. The Irritability domain includes: bad temper, rapid mood changes, sudden anger, impatience, crankiness, argumentativeness. The Aggression domain includes: getting upset, resisting activities, stubborn, uncooperative, hard to handle, shouts, curses angrily, slams doors, kicks furniture, throws things, hurts or hits others.

The NPI has established content and concurrent validity, as well as inter-rater (approximately 95% for both frequency and severity), test-retest (0.79 for frequency and 0.86 for severity), and internal consistency reliability (Cronbach’s alpha of 0.88 for both).¹⁰⁴ The NPI-Distress has established content and concurrent validity, and inter-rater (0.96), test-retest (0.92), and internal consistency reliability.¹⁰⁵

Few scales exist to specifically assess irritability in neurologic disorders. Other available measures ask only about the presence or frequency of irritability. Only the NPI assesses the distress caused by the irritability. This multifaceted assessment of the problem makes the NPI ideal for the study of irritability in TBI, and specifically in this medication trial.

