Hypothesis 1b: Among individuals with TBI of >6 months duration, BUSP will result in statistically significant improvement in scores of one or more of the following measures compared to placebo: a) observer and participant ratings of NPI and NPI-Distress Irritability domain scores, b) observer and participant ratings of NPI and NPI-Distress Aggression domain scores, c) participant ratings of TBI-QOL Anger bank, d) observer ratings of SASNOS, e) observer and participant ratings of Global Impression of Change, f) physician ratings of Clinical Global Impressions.

The primary analysis will be intention-to-treat. For Hypothesis 1a, the primary outcome, the percent of participants who are considered to have meaningful reduction in irritability (decrease of at least 3 points in the NPI Irritability Domain Score) from baseline to 91 days, will be compared between the two groups (those receiving active drug and

placebo) using a chi-square test. A logistic regression model will be used to adjust for depression and possible demographic and baseline differences between the two groups and a post-hoc secondary analysis will examine the factors (including depression and anxiety) influencing the effect of BUSP on the primary outcome by including group interaction in the logistic model. For Hypothesis 1b, the change in the observer-rated NPI Irritability Domain Score from baseline to 91 days will be compared between the two groups using a Wilcoxon rank sum (Mann-Whitney) test for ordered categories. The secondary outcomes will also be compared between the two groups using Wilcoxon rank sum tests. For the secondary outcomes, Hochberg's step-up Bonferroni method will be used to control for multiple testing. Secondary analyses will include repeating the analyses above using the PPS population. Wilcoxon rank sum tests will also be performed for separate subgroups such as females, males, participants with injury caused by motor vehicle crashes or falls to test whether BUSP can be efficacious for these separate subgroups. In addition, if a substantial number of participants have depression, a preliminary analysis of the effect of BUSP on PHQ-9 may be performed. The effect of BUSP on GAD-7 will also be performed.

Safety Analysis: Hypothesis 2: BUSP will be tolerated as measured by number and types of the adverse events in the treatment group compared to the placebo group.

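### The exploratory test of whether depression or anxiety modifies the buspirone effect uses only the dichotomised responder outcome; an interaction on the full NPI Irritability change would use the same data better

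*Combined protocol and SAP*

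**What the plan says.** The relevant text is in Section 8.1, Efficacy Analyses. The primary outcome is "the percent of participants who are considered to have meaningful reduction in irritability (decrease of at least 3 points in the NPI Irritability Domain Score"), compared between arms by chi-square. A logistic model then adjusts for depression and for baseline differences. Effect modification comes next. The plan announces it in these words: "a post-hoc secondary analysis will examine the factors (including depression and anxiety"). The method it gives is an interaction term in the responder model, to look for anything "influencing the effect of BUSP on the primary outcome by including group interaction in the logistic model".

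The score behind the responder definition is finer than yes/no. Section 5.1 says "the product (severity x frequency) is calculated (range 0-12"), and adds: "A secondary analysis compares changes in NPI-Irritability using an ordinal scale". Section 8.1 carries that out as a two-group rank-sum comparison: "the change in the observer-rated NPI Irritability Domain Score from baseline to 91 days will be compared between the two groups using a Wilcoxon rank". It has no interaction term.

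The only other effect-by-subgroup analysis is: "Wilcoxon rank sum tests will also be performed for separate subgroups such as females, males, participants with injury caused by motor vehicle crashes or falls". These are separate tests within subgroups, and neither depression nor anxiety is named. The planned PHQ-9 and GAD-7 analyses treat those scales as outcomes, not as moderators.

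Depression is also the stratifier: "Randomization will be stratified on the presence of major or minor depression (defined by PHQ-9 total score ≥ 5"). The documents do not give the expected share above that cut, the coding of depression and anxiety in the interaction model (binary or continuous), the interaction test to be used, or a fallback if a cell is empty of responders or of non-responders.

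**The concern.** Section 5.1 defends the 3-point cut as a way to show clinical as well as statistical significance in the primary comparison. That reason does not carry over to the question of who benefits more, where no clinical threshold is claimed. An interaction is estimated much less precisely than a main effect, and cutting a 0-12 change into two classes discards further information.

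There is a second, conditional difficulty. If the moderator is coded as present/absent, the interaction rests on four cells. When one cell contains only responders or only non-responders, the maximum-likelihood interaction odds ratio is not finite and its Wald test is uninformative.

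At stake is the quality of an exploratory result. It has one stated use: Section 5.1 makes noting anxiety change depend on whether baseline anxiety is associated with response to study drug.

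**Working it through.** **The plan's own figures.**
- Chi-square, 40% vs 80%, 90% power, two-sided 0.05, pooled variance in both terms: n = (1.960 + 1.282)² × 2 × 0.6 × 0.4 / 0.4² = 31.5, so 32 per group. The usual formula gives 30 without and 35 with continuity correction. The stated 33 lies among these, and exact chi-square power at 33 per group is 94.0%.
- Noether, P(Y>X) = 0.70, 80% power: (1.960 + 0.842)² / (12 × 0.25 × 0.20²) = 65.4 in total, so 33 per group, as stated.
- Dropout: 33 / 0.90 = 36.7, so 37 per arm, as stated.

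**Effect sizes implied by the plan, under a normal latent change.**
- 40% vs 80%: z(0.80) − z(0.40) = 0.842 + 0.253 = 1.095 SD.
- P(Y>X) = 0.70: √2 × z(0.70) = 1.414 × 0.524 = 0.74 SD.

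**Assumptions not in the documents.** Moderator prevalence 50%, 65% or 80%; buspirone works only in those with the moderator; change SD 3.5 points; baseline spread equally over 6, 8, 9 and 12; scores on the attainable NPI values 0, 1, 2, 3, 4, 6, 8, 9, 12.

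**Hand check of full-scale interaction power, 33 per arm.** With prevalence f, the standard error in SD units is √(2/(33f) + 2/(33(1−f))). At f = 0.5 this is √(0.1212 + 0.1212) = 0.492, so power is Φ(1.095/0.492 − 1.96) = Φ(0.26) = 60%. The coarse, bounded NPI score should bring this down somewhat, and it does in the simulation below.

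**Simulated interaction power, 33 per arm, effect 40% vs 80%.** Data sets with an infinite estimate count as not significant on the Wald test.

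| Prevalence | Logistic, Wald | Logistic, likelihood ratio | Full-scale change |
|---|---|---|---|
| 50% | 36% | 45% | 57% |
| 65% | 37% | 41% | 53% |
| 80% | 27% | 30% | 41% |

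In this run the full scale leads the likelihood-ratio test by 12, 12 and 11 points, and the Wald test by 21, 16 and 14. A second simulation, with the full-scale model adjusted for baseline, gave 27-36% (Wald), 30-42% (likelihood ratio) and 41-54% (full scale). Allowing for such differences, the loss is about 10-15 points on the likelihood-ratio test and about 14-19 on the Wald test.

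**Smaller effect, 0.74 SD, through the same data model.** Logistic about 14-23%, full scale about 21-28%: a loss of about 4-8 points.

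**Continuous moderator.** Logistic 33-40%, full scale about 49%.

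**False positives with no interaction.** Likelihood ratio 6-8%, Wald 2-4%, full scale near 5%. The full-scale gain is not bought with a higher error rate.

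**Chance of an all-or-none cell.** This takes a binary moderator, 80% vs 40% response at both levels, and m and M per arm in the two levels. P = 1 − Π(1 − pᵏ − (1−p)ᵏ) over p = 0.8, 0.4 and k = m, M. For 33 per arm at 80% prevalence, m = 7 and M = 26. The small buspirone cell contributes 0.8⁷ = 0.210, the small placebo cell 0.4⁷ + 0.6⁷ = 0.030, and the large buspirone cell 0.8²⁶ = 0.003. So P = 1 − 0.790 × 0.970 × 0.997 = about 0.24. Across 33 and 37 per arm the result is 3-5% at 50% prevalence, 6-8% at 65% and about 23% at 80%.

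**The case against.** The strongest reply is about status. The analysis is labelled post-hoc and secondary; no hypothesis, alpha or sample-size claim depends on it; and Section 8.1 already allows further exploratory analyses. All of that stands and keeps the point modest. It does not make the responder model the better choice.

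A reader might infer that effect modification by depression is a leading question of the trial because randomisation is stratified on it. The documents do not support this. Section 4.1 stratifies for balance between arms, and says the study is neither designed nor powered to examine the effect on depression.

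A reader might also infer that the logistic model will probably return no estimate. That is too strong. The four-cell argument needs a binary coding that the plan does not state; continuous PHQ-9 and GAD-7 totals could enter the model as written, and the problem is then smaller. Even with binary coding, failure is uncommon unless one level is small. Section 4.1 calls depression common after TBI and the PHQ-9 cut of 5 takes in the mild band, so an uneven split is plausible, but no prevalence is given.

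A third objection is that the power advantage assumes 1.095 SD, whereas the plan sizes its Wilcoxon tests at P(Y>X) = 0.70. At 0.74 SD the normal approximation gives full-scale power of only 33%, 30% and 23%, below the logistic figures in the table. But that sets a smaller effect on one scale against a larger effect on the other. When the same 0.74 SD shift drives both analyses, the full scale still leads, by less.

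Finally, an interaction on the responder scale fits Hypothesis 1a and tells the reader who becomes a responder. That is a fair reason to keep it, though not as the only version.

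**Conclusion.** The point holds as an improvement to an exploratory analysis. For depression and anxiety, the only planned interaction is on the dichotomised outcome. At 33 per arm this costs about 10-15 points of power (likelihood ratio) or about 14-19 (Wald) if the effect is 40% vs 80%, and about 4-8 on either test if it is P(Y>X) = 0.70. The sizes depend on the assumed prevalence, change SD, baseline mix and an all-or-nothing interaction. The direction was the same in every scenario tried, including a continuous moderator.

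The sparse-cell risk is secondary and conditional on binary coding.

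Two further inferences would be wrong. The primary chi-square test on responders is unaffected. And the full-scale interaction would not make the moderator question confirmatory: its own power is only about 20-55% in these scenarios, so much of the chance of missing a modifier comes from the sample size, not from the model.

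**What to change.** In Section 8.1, Efficacy Analyses, after the sentence on the logistic interaction:

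- Add group-by-baseline PHQ-9 and group-by-baseline GAD-7 interactions, with total scores as continuous moderators, in a linear or proportional-odds model of the observer-rated NPI Irritability change from baseline to Day 91, adjusted for baseline NPI Irritability. Name one of the two model forms in advance.
- Report interaction estimates with confidence intervals and label them exploratory.
- Keep the logistic interaction as a companion on the responder scale, fitted by Firth penalised likelihood so that a cell with all or no responders still gives a finite estimate. State how the moderators are coded.
- Leave the primary chi-square test unchanged.

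The cost is a few lines of text and one extra model per moderator, on data already collected at baseline and Day 91. The added result is in NPI points rather than responder odds, which is why the two should be shown side by side.

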- **St Andrew's-Swansea Neurobehavioural Outcome Scale (SASNOS):**¹¹⁵ SASNOS is a newly developed informant-rated measure designed specifically to assess neurobehavioral dysfunction in acquired brain injury as rated by an observer. SASNOS has a 5-factor conceptual framework based on the World Health Organization International Classification of Function (WHO ICF) that allows the measurement of a diverse range of NBD signs and symptoms in the following domains: interpersonal relationships, cognition, aggression, inhibition and communication. Initial validation suggests that the 49-item SASNOS is reliable and valid. The proposed study will utilize the aggression subscale, which includes 15 items and three subfactors: overt aggression (3 items), irritability (6 items), and provocative behavior (6 items). The aggression subscale demonstrates excellent test-retest reliability (ICC=.92) and internal consistency (alpha=.92), good inter-rater reliability (ICC=.80), and a strong statistical relationship with known measures, supporting its content, convergent, and divergent validity.

- **Global Impression of Change (GIC):** A Likert Scale rating impression of change (much improved, slightly improved, no change, slightly worse, or much worse) will be used for both participants and observers to rate their impression of change in the person with TBI.

- **Clinical Global Impressions (CGI):** The clinician's impression of change will be determined using the CGI. The CGI¹⁵⁸ is a highly sensitive,¹⁵⁹ standardized assessment tool used widely to assess psychopharmacology treatment response. The CGI is comprised of 3 subscales: Severity of Illness (SI), Global Improvement (GI), and Efficacy Index (EI). SI and GI are both rated on 7-point scales. The EI is rated on a 4-point scale that takes into account both beneficial effects and side effects. The CGI is rated by a clinician/investigator. The SI subscale is administered at initial assessment and then all three subscales are administered at follow-up assessments. To be considered effective, a treatment should lower the overall score in subsequent testing by at least 50%.¹⁶⁰ The CGI takes approximately 2 minutes for the clinician to score.

Experimental Measure (this measure to be developed after study completion, and thus, will be delayed in time from final analysis)

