- **Aggression and Irritability Impact Measure (AIIM):** The AIIM is an experimental measure that will be developed and evaluated through the companion measurement study. It will consist of items assessing the degree to which irritability or aggression interferes with community participation activities. Specific community participation activities will be represented by items of the Participation Assessment with Recombined Tools-Objective (PART-O).¹⁶¹ Additional items may be added after focus group review and cognitive interviewing that will take place prior to launching the study. The AIIM will be designed to assess specifically the degree to which irritability and aggression interfere with participation in contrast to the PART-O which assesses the extent of community participation in general. The beta version of the AIIM will be included in this Buspirone treatment study. It will be administered at the Baseline and Final visits as it is thought that the longer period is needed to allow time for changed impact. After refining it through psychometric studies, the final version of the AIIM will be extracted from the Beta version and analyzed as a dependent measure in the treatment arm to assess its responsiveness to the hypothesized treatment effect. The AIIM is included in the treatment arm only to assess its responsivity and not as an endpoint.

- **Working Alliance Inventory-Short Revised (WAI-SR):** The WAI-SR is a 12 item questionnaire with forms for completion by the person receiving treatment as well as by the provider. This measure of working or therapeutic alliance has been shown to predict the outcome of psychotherapeutic as well as rehabilitation interventions.²¹⁹ The WAI-SR is based on a factor analysis of the full WAI and has demonstrated reliability and validity.²²⁰ The WAI-SR will be completed during the post-treatment assessment session at the end of the buspirone trial by the participant and by the research assistant who worked with the participant in the trial. Each of these individuals will complete the inventory independently without knowledge of each other's responses. Data obtained from the WAI-SR will be evaluated as a covariate in analyses of outcome variables to assess for effects of buspirone relative to placebo.

Stratification Measure

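### The Hypothesis 1b Wilcoxon tests leave out the baseline score as a covariate and the PHQ-9 stratum; adding both is a free gain in power, and the post-treatment WAI-SR should not be a covariate

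*Combined protocol and SAP*

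**What the plan says.** Section 4.1 (Stratification): "Randomization will be stratified on the presence of major or minor depression", with PHQ-9 of 5 or more as the cut. The reason given there is that depression is common after TBI and that irritability is one of its main symptoms.

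Section 8.1 (Efficacy Analyses) compares change in observer-rated NPI-Irritability between arms by a two-group Wilcoxon test. It then adds: "The secondary outcomes will also be compared between the two groups using Wilcoxon rank sum tests". It does not say whether those other scores are tested as change or as Day 91 values. Section 5.1 (Outcome Variables) mentions change only for the same domain: "A secondary analysis compares changes in NPI-Irritability using an ordinal scale". Hochberg's method is applied across the secondary outcomes.

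The Visit 1 list and the Schedule of Events (section 5.1) show baselines for NPI, NPI-Distress, TBI-QOL Anger and SASNOS. For the CGI, "The SI subscale is administered at initial assessment and then all three subscales are administered at follow-up assessments". So only CGI Severity has a baseline, while CGI Global Improvement, the CGI Efficacy Index and both GIC ratings have none.

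For Hypothesis 1a the sized test is a chi-square. A logistic model adjusts for depression and for such between-arm differences as may appear.

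On the Working Alliance Inventory, section 5.1 says "Data obtained from the WAI-SR will be evaluated as a covariate in analyses of outcome variables" and also "The WAI-SR will be completed during the post-treatment assessment session at the end of the buspirone trial". The same section lists it among the secondary efficacy measures ("Short Revised rated by participant and Co-Investigator").

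**The concern.** A baseline that correlates with the Day 91 score explains part of its variance. Subtracting baseline uses that information well only when the correlation is high; testing Day 91 alone does not use it at all. The plan itself treats depression as prognostic by stratifying on it, yet adjusts for it only in the Hypothesis 1a logistic model.

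Power is scarce on these scores. The secondary sample size gives 80% for one test at 0.05, but Hochberg covers 13 tests, or 15 if all three CGI subscales are tested. If only one score truly responds, it must clear roughly 0.05/13 or 0.05/15.

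The WAI-SR raises a different issue. It is completed after treatment, so if alliance ratings rise as patients improve, adjusting for it removes part of the effect being estimated.

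**Working it through.** **1. The plan's own figure.** Inputs from section 8.1 (Sample Size): P(Y>X) = 0.70, alpha 0.05, power 80%. Noether, two-sided: N = (1.960 + 0.842)² / (12 × 0.25 × 0.20²) = 65.4, i.e. 33 per arm. Power at 33 per arm is Φ(√(3 × 66) × 0.20 − 1.960) = 80.4%. The stated 33 reproduces, with no covariate or stratum term. With the same effect, power is about 47% at 0.05/13 and 45% at 0.05/15. That is Hochberg's worst case; if every score responds, 0.05 can suffice.

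**2. Family size.** NPI and NPI-Distress Irritability by two raters 4, Aggression likewise 4, TBI-QOL Anger 1, SASNOS 1, GIC 2, CGI 1 or 3: total 13 or 15.

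**3. Gain from baseline.** The documents do not give r, so it is assumed. Take SD 1 at both times and a 0.6 SD shift at Day 91. The working SD is √(2(1 − r)) for change, 1 for Day 91 alone, and √(1 − r²) with baseline as a covariate. Put P = Φ(0.6 / (SD × √2)) into power = Φ(√198 × (P − 0.5) − 1.960).

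| r | Change: SD, P, power | Day 91: P, power | Baseline-adjusted: SD, P, power |
|---|---|---|---|
| 0.3 | 1.183, 0.640, 50% | 0.664, 64% | 0.954, 0.672, 68% |
| 0.5 | 1.000, 0.664, 64% | 0.664, 64% | 0.866, 0.688, 75% |
| 0.7 | 0.775, 0.708, 83% | 0.664, 64% | 0.714, 0.724, 88% |

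Simulation agrees: about 48/65/86% for Wilcoxon on change (repeat runs 50–51% at r = 0.3), 65/64/65% on Day 91, and 67/74/89% for rank-ANCOVA with baseline and stratum. Null rejection was near 5% for all three.

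**4. Observer NPI-Irritability.** This score is coarse (products of severity and frequency) and limited to 6 or more at entry. With nine equally likely product values and a 0.6 SD shift, power was 59/71/87% for Wilcoxon on change and 67/75/88% for rank-ANCOVA: gains of 8, 4 and 1 points. A separate coarse-scale simulation gave about 0 to 4 points for r from 0.1 to 0.7.

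**5. Stratum alone.** Let it explain a share R² of residual variance (assumed). Starting from 80.4%, power becomes 81.1, 82.1 and 83.9% at R² of 0.02, 0.05 and 0.10, a gain of 0.7 to 3.5 points. For a five-level GIC with P = 0.70 and a depression effect of 0, 0.5 or 1.0 SD, Wilcoxon gives 80/79/72% and van Elteren 80/80/79%. Wilcoxon's null size is then 4.9/4.5/3.0%: conservative, not inflated.

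**6. Where adjustment does not pay.** At r = 0.9 on continuous scores with P = 0.70 on change, rank-ANCOVA gave 77.8% against 82.6% for Wilcoxon on change (stratum not prognostic), and 82.0% against 82.8% with R² = 0.10. At r = 0 with a 0.6 SD shift it gave 64%, against 65% for Wilcoxon on Day 91.

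**7. WAI-SR.** At r = 0.5, let WAI-SR correlate 0.3 or 0.5 with improvement within arm (assumed). The mean treatment coefficient moves from −0.74 to −0.69 or −0.59. Shrinkage is 0.05/0.74 = 7% or 0.15/0.74 = 20%, and rank-ANCOVA power falls from 90% to 88% or 82%.

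**8. Hypothesis 1a model.** A single-step fall in severity or frequency from 12 (to 8 or 9) or from 9 (to 6) is always at least 3 points. From 8 (to 4 or 6) or 6 (to 3 or 4), only one of the two steps is. Baseline is therefore a natural covariate. Even so, logistic regression with stratum and baseline changes power by only −0.4 to +2.3 points against chi-square at 40% versus 80%. Its likelihood-ratio test rejects 5.6–6.3% under the null.

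**The case against.** The strongest reply is that this is a preference. The outcomes are ordinal, the rank tests are justified and sized in section 8.1, multiplicity is controlled, and the plan meets its own 80% target unadjusted. That stands as far as it goes: nothing here is an error. It does not remove the point, because the information is already collected and using it costs only wording.

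Two further objections limit the size. The gain comes almost entirely from baseline, not from the stratum. And because section 8.1 leaves change or Day 91 open for all scores but one, no single figure applies: at r = 0.3 the gain is about 19 points over change (67 − 48) but about 2 over Day 91 (67 − 65), while at r = 0.7 it is about 3 (89 − 86) and about 24 (89 − 65).

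On WAI-SR, it is fair to say that section 8.1 writes down no model containing it and that a Wilcoxon test has no place for a covariate. The stated intention in section 5.1 remains, however, and should be withdrawn or confined to exploratory work.

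A reader might infer that ignoring the randomisation stratum makes the tests invalid or biased. It does not: null size stays at or below about 5% when the stratum is prognostic. Nor is baseline ignored altogether, since the observer NPI-Irritability test is on change.

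**Conclusion.** A free improvement. The Hypothesis 1b tests are valid and meet the stated single-test power, but use neither baseline as a covariate nor the PHQ-9 stratum. Under the assumptions in the working (33 per arm, normal scores, 0.6 SD shift, r from 0.3 to 0.7), rank-ANCOVA adds about 3 to 19 points over Wilcoxon on change and about 2 to 24 over Wilcoxon on Day 91. For observer NPI-Irritability the gain is about 0 to 8 points for r up to 0.7. The stratum alone adds about 0 to 4 unless depression is very strongly prognostic. On continuous scores with r near 0.9 and a stratum that is not prognostic, there is no gain or a small loss. Neither r nor the prognostic strength of depression is in the documents.

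The one risk of bias is the WAI-SR covariate, and its size depends on an assumed correlation with improvement. The open covariates for Hypothesis 1a are a minor matter in a supporting model. The documents do not support reading this as a threat to the primary chi-square or as a failure of the sample size.

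**What to change.** Before unblinding, amend the SAP text:

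1. Test each Hypothesis 1b score that has a baseline (including CGI Severity, if tested) by rank-ANCOVA of the Day 91 score on treatment, its own baseline and PHQ-9 stratum (5 or more versus below). Test both GIC ratings, CGI Global Improvement and the CGI Efficacy Index by a van Elteren test stratified by PHQ-9. Report P(Y>X) or medians beside each p-value, since rank-ANCOVA estimates are on the rank scale. Define the Hochberg family as the Hypothesis 1b list, 13 tests or 15 with all three CGI subscales, and state that WAI-SR lies outside it.
2. Do not use WAI-SR as a covariate in any treatment-effect estimate; keep any WAI-SR analysis exploratory.
3. Minor: keep the chi-square as the confirmatory Hypothesis 1a test. Fix the logistic model to treatment, PHQ-9 stratum and baseline observer NPI-Irritability, with no covariates chosen from observed imbalance. Because its likelihood-ratio test runs slightly above 5%, label it a sensitivity analysis.

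The cost is wording only: no new data or patients, and no change to the primary test. The downside is a possible small loss of power on a score whose r is near 0 or 0.9.
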